7 STUDY OBJECTIVES AND ENDPOINTS

7.1 Primary objective(s)

The primary objective(s) of the study is to evaluate each subject's plasma concentrations of nicotine after administration of one single dose of ZYN® Smooth containing 6 mg of nicotine, to that of one single dose of 2x1 pouches of General PSWL Swedish snus.

7.1.1 Primary endpoint(s)

AUC_{inf} based on plasma concentrations of nicotine after administration of a single dose of ZYN® Smooth containing 6 mg of nicotine, to that of two doses of General PSWL Swedish snus pouches.

7.2 Secondary objectives

The secondary objectives of the study are to evaluate pharmacokinetic variables for the remining products, plasma levels of Methyl salicylate and local tolerability.

1. To compare T_{max}, C_{max}, AUC_{inf}, AUC_{0-t} from each dose of the non-tobacco-based nicotine ZYN[®] Smooth pouches, General PSWL Swedish snus pouches and Longhorn American moist snuff pouches.

- 2. To assess the effect of the flavour component (Methyl salicylate) on nicotine plasma concentrations for the non-tobacco-based nicotine pouch ZYN® Wintergreen and Longhorn Wintergreen pouch American moist snuff, respectively.
- 3. To assess if there is a difference in nicotine plasma concentrations between upper lip and lower lip placement of the non-tobacco-based nicotine pouch ZYN® Smooth.
- 4. To compare the estimated *in-vivo* extracted amount and rate of extraction of nicotine from each dose.
- 5. To assess plasma levels of Methyl salicylate for the treatments with pouches containing Wintergreen flavour.
- 6. To compare Adverse events from each dose.

7.2.1 **Secondary endpoints**

- 1. T_{max} , C_{max} , AUC_{inf} , AUC_{0-t} and terminal half-life of the non-tobacco-based nicotine ZYN^{\otimes} Smooth pouches, General PSWL Swedish snus pouches and Longhorn American moist snuff pouches.
- 2. Nicotine plasma concentrations for the ZYN® Wintergreen and Longhorn Wintergreen treatments compared to the corresponding non-wintergreen containing product, respectively.
- 3. Nicotine plasma concentrations for the upper lip and lower lip placement of the non-tobacco-based nicotine pouch ZYN® Smooth.
- 4. *In-vivo* extracted amount of nicotine from all products.
- 5. Pairwise analysis of in-vitro extracted nicotine and rate of extraction.
- 6. To analyze plasma levels of Methyl salicylate for the treatments with pouches containing Wintergreen flavour.
- 7. Collection and comparison of adverse events

8 STUDY DESIGN

8.1 Overall study design and schedule of events

The study will be conducted as an open, randomized, seven-way cross-over, single dose administration. The study will include 36 subjects.

The subjects included will be healthy males and females aged ≥ 19 years who have used tobacco-based snus for ≥ 1 year with a weekly consumption of three or more snus cans (brands with nicotine content $\geq 1\%$). Subjects who are pregnant or who have a history of hypertension or any cardiovascular disease are excluded. Subjects shall be abstinent from snus and all other nicotine containing products from 8.00 p.m. the night before each trial day.

Before entry to the study subjects undergo screening, evaluations including smoking and snus use, medical history and collection of height and weight.

Subjects report to the clinic on separate days for the seven (7) experimental sessions in addition to visits for screening and follow-up. Between each experimental session a washout period of at least 24 hours is required. The subjects are instructed to abstain from snus or other nicotine delivery products as from 8.00 p.m. the evening before and to refrain from smoking 24 hours before each experimental session. All sessions are performed during the morning hours to facilitate abstinence. The subjects should certify abstinence before each treatment is started.

The treatments are administered as single doses in a pre-determined randomized order. The subject keeps the pouch still between the upper lip (lower lip for treatment 4) and the gum for 60 minutes and are instructed not to manipulate the pouch with the tongue or lips. The subjects are instructed not to eat, drink, chew chewing gum or brush teeth from 30 minutes before application of treatment, during application of investigational products and 30 minutes after the investigational product have been taken out (Henningfield et al 1990)³.

After 60 minutes the pouches are collected and frozen (-20°C) pending analyses of nicotine.

Blood samples for assessment of plasma levels of nicotine and Methyl salicylate will be collected at pre-defined time points from pre-dose to 6 hours after IP administration.

Table 8.1-1 Schedule of events

Visit	Visit 1 ¹ Screening	Visit 2-8 ² Cross-over	Visit 9 Telephone FU
Assessments / Study days	-28 to -1		7 days(-3/+7) after last dose
Informed consent	x		
Demographics	X		
Medical/surgical history	x		
Inclusion/exclusion criteria	x		
Physical examination	x		
Weight, height	x		
HIV, Hepatitis B and C	x		
Pregnancy test ³	X		
Drugs of abuse	X	x ⁴	
Alcohol screen	x	x ⁴	
CO measurement	X	x	
Randomisation		x ⁵	
IP (pouch) administration		x	
PK blood sampling		x ⁶	
Collection of pouches		х	
Treatment-emergent AEs (TEAEs)8		x	x
Baseline events	X	x ⁷	
Prior and concomitant medications ⁹	X	x	X

¹ Visit 1 could be performed during 2 days

² Refer to section 8.1.3, Schedule of Events per visit for, details.

³ Female subjects only

⁴ Drug and alcohol tests during the treatment period may be performed randomly.

⁵ Only on visit 2

⁶ Before and 5, 10, 15, 30, 60, 90, 120, 240 and 360 min after application of the investigational products

⁷Only prior to dose administration at Visit 2.

⁸ From first administration of IP.

⁹ For definitions of prior and concomitant medication, see Section 10.2.7.

Table 8.1-2 Detailed schedule of events for each treatment period

Visit					V	Visit 2 to 8	∞					
Assessment/time-point	Admission	Pre- dose	•	min 5	10	15 min	min	min	min	2 h	4 h	6
Inclusion/exclusion criteria	x ¹											
CO measurement	×											
Drugs of abuse	x ²											
Randomisation		X ³										
IP (pouch) administration			×									
IP (pouch) collection								X ⁴				
PK blood sampling		×		×	×	×	×	×	×	×	×	
Treatment-emergent AEs (TEAEs)							×					
Prior and concomitant medications						×						

¹ Confirmation of inclusion/exclusion criteria (Visit 2 only).

MW001TEMP01_02CSP

² Drug tests during the treatment period may be performed randomly
³ Only on visit 2

⁴ Collection of pouch +/- 1 (one) minute from specified time.

8.2 Rationale for study design

A crossover design was chosen to yield a more efficient comparison of treatments than a parallel study design, i.e., fewer subjects are required since each subject will serve as his own control. To avoid carryover effects, a wash-out period of at least 24 hours has been incorporated between administrations.

Randomisation will be used to minimise bias in the assignment of subjects to a treatment sequence and to increase the likelihood that known and unknown subject attributes (e.g., demographic and baseline characteristics) are evenly balanced across treatment groups.

Prospective approval of protocol deviations to eligibility criteria, also known as protocol waivers or exemptions, is not permitted.

8.3 Recruitment

The subjects will be recruited from a list of healthy volunteers at CTC and from advertising in media.

8.4 Screening and enrolment log

Investigators must keep a record of all screened subjects even if they were not subsequently included in the study. This information is necessary to verify that subjects were selected without bias. The reason for screen failure should be stated for all subjects screened but not included. The reason for withdrawal should be stated for all subjects included but not completed.

A screening number will be allocated to each subject in connection to the informed consent process at the Screening visit. The screening number is generated automatically in the electronic case report Form (eCRF). The screening number will allow identification of subjects irrespective of their possible eligibility for the study.

Subjects included and randomised will be assigned a randomisation number (101,102 and 103 etc.).

8.5 Number of subjects

36 subjects will be included in the study.

For replacements of subjects discontinuing the study, see Section 8.5.

8.6 Inclusion criteria

For inclusion in the study, subjects/patients must fulfil the following criteria:

- 1. Snus user who have used snus for ≥ 1 year, with a minimum weekly consumption of two or more snus cans (preferably brands with nicotine content $\geq 1\%$).
- 2. Willing and able to give written informed consent for participation in the study.
- 3. Healthy male or female subject aged \geq 19 years of age inclusive.
- 4. Willing and able to comply with study procedures.

8.7 Exclusion criteria

Subjects must not enter the study if any of the following exclusion criteria are fulfilled:

- 1. Smoker, defined as "smoking during the last 24 hours according to self-report and CO in exhaled air >10 ppm at clinical visits.
- 2. A history or presence of diagnosed hypertension or any cardiovascular disease.
- 3. Surgery within 6 months of the screening visit that, in the opinion of the investigator, could negatively impact on the subject's participation in the clinical study.
- 4. Any surgical or medical condition, which, in the judgment of the clinical investigator, might interfere with the absorption, distribution, metabolism or excretion of the investigational product.
- 5. History of any clinically significant disease or disorder which, in the opinion of the Investigator, may either put the subject at risk because of participation in the study, or influence the results or the subject's ability to participate in the study.
- 6. Breast feeding, pregnancy or planning to get pregnant during the study.
- 7. Female use of systemic contraceptives (such as oral contraceptives, implants, injectable steroids, vaginal ring, transdermal patch).
- 8. Any positive result on screening for serum hepatitis B surface antigen, hepatitis C antibody and Human Immunodeficiency Virus (HIV).
- 9. Positive screen for drugs of abuse or alcohol at screening or on admission to the unit prior to administration of the IP.
- 10. Current or history of alcohol abuse and/or use of anabolic steroids or drugs of abuse.
- 11. Plasma donation within one month of screening or blood donation (or corresponding blood loss) during the three months prior to screening.
- 12. Investigator considers the subject unlikely to comply with study procedures, restrictions and requirements.

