8.8.1 General restrictions

- Subjects shall abstain from snus and all other nicotine containing products from 8.00 p.m. the night before each study day.
- Subjects shall abstain from smoking the last 24 hours before each study day.
- The subjects are not allowed to eat or drink or use any other mouth related procedure (e.g. tooth brushing) 30 minutes before dose administration, during application of investigational products and 30 minutes after the investigational product have been taken out. ³.
- The female volunteers are expected to be sexually abstinent or use non-systemic contraceptives to prevent pregnancy during the study period.

- Abstain from use of Methyl salicylate containing products, e.g. ointments, mouth wash and chewing gum.
- Abstain from drugs of abuse from Screening to the Follow-up visit.
- The subjects must not donate blood or plasma during the study until three months after the Follow-up Visit.
- Study subjects are not allowed to participate in any other clinical study during the study period i.e screening to follow up.

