8.10 Criteria for subject/patient withdrawal

8.10.1 General withdrawal criteria

Subjects are free to discontinue their participation in the study at any time and for whatever reason without affecting their right to an appropriate follow-up investigation or their future care. If possible, the reason for withdrawal of consent should be documented.

Subjects may be discontinued from the study at any time at the discretion of the Investigator for any of the following reasons:

- Severe non-compliance to study protocol procedures, as judged by the Investigator and/or Sponsor
- Subject is lost to follow-up. A subject will be considered lost to follow-up if he/she fails to come for 2 number of scheduled visits and if he/she is not possible to contact by site staff despite several attempts.
- Significant AEs posing a risk for the subject, as judged by the Investigator and/or Sponsor

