10.2.13 Carbon monoxide measurement

Measurement of carbon monoxide (CO) in exhaled air will be performed at visits to the clinic.

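### Exclusion criterion 1 joins self-report and exhaled CO with 'and', so read literally neither a raised CO alone nor admitted smoking alone meets it

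*Protocol*

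**What the plan says.** Section 8.7 opens with "Subjects must not enter the study if any of the following exclusion criteria are fulfilled". Criterion 1 then describes a smoker as "smoking during the last 24 hours according to self-report and CO in exhaled air >10 ppm at clinical visits". The synopsis has the same wording.

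Three other places deal with smoking or CO:

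- Section 8.8.1: "Subjects shall abstain from smoking the last 24 hours before each study day". Section 8.1 gives the same 24-hour rule for each experimental session and adds "The subjects should certify abstinence before each treatment is started".
- Section 10.2.13: "Measurement of carbon monoxide (CO) in exhaled air will be performed at visits to the clinic". It gives no threshold and no consequence.
- Tables 8.1-1 and 8.1-2 schedule CO at screening and on admission at each of Visits 2 to 8. A footnote to Table 8.1-2 has the eligibility criteria re-confirmed at Visit 2 and at no later visit.

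The 10 ppm threshold appears only in criterion 1.

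**The concern.** An objective test is added to self-report so that it can contradict the subject's account. When the two are joined by 'and', the test can only shrink the group already identified by self-report. It cannot add anyone to it.

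This matters because the primary endpoint is nicotine AUCinf (Sections 7.1.1 and 16.5.1), and a cigarette is another source of the substance being measured. Nicotine inhaled shortly before a session would be present in plasma and could be counted as exposure from the pouch. The protocol evidently regards this as worth guarding against, since it requires abstinence and measures CO at every clinic visit. The written rule does not make use of that measurement.

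**Working it through.** No sample size, power or alpha figure bears on this point. The check is of the logic of the rule, followed by a count of the readings it governs.

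**Step 1: criterion 1 as a rule.** There are two inputs, each yes or no.

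| Reports smoking in last 24 h | CO >10 ppm | Meets criterion 1 with 'and' | Meets criterion 1 with 'or' |
|---|---|---|---|
| Yes | Yes | Yes | Yes |
| Yes | No | No | Yes |
| No | Yes | No | Yes |
| No | No | No | No |

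As written, one of the four combinations excludes; with 'or', three do. The lead-in to Section 8.7 lets any single criterion exclude, but that works between criteria and does not separate the two elements inside criterion 1.

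**Step 2: criterion 1 beside the smoking restriction.** The second row is a subject who admits smoking within 24 hours. Sections 8.1 and 8.8.1 forbid this before a session, yet criterion 1 does not exclude that subject when CO is 10 ppm or less. The entry rule is therefore looser than the restriction that applies once the subject is in the study.

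**Step 3: does another passage attach a consequence to CO?**

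- Section 10.2.13 and both schedules state only that CO is measured.
- Section 8.8.1 carries no CO rule.
- Section 8.1 rests abstinence at sessions on the subject's certification.
- Criterion 12 covers a case where the "Investigator considers the subject unlikely to comply with study procedures, restrictions and requirements". It does not name CO.
- Section 8.10.1 allows withdrawal for "Severe non-compliance to study protocol procedures, as judged by the Investigator and/or Sponsor". It does not name CO.
- Section 16.3.2 has deviations judged major or minor at the clean file meeting. It does not name CO.

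For contrast, criterion 9 lets a positive drug or alcohol screen exclude on its own.

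**Step 4: which readings are affected.** Counting the 36 subjects of Section 8.5, with no drop-out:

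- All planned readings: 36 × (1 screening + 7 sessions) = 36 × 8 = 288.
- Readings that bear on entry (screening and Visit 2): 36 × 2 = 72.
- Readings at Visits 3 to 8: 36 × 6 = 216.

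For the 72, criterion 1 applies but a raised CO does not suffice. For the 216, no stated rule applies, although criterion 1 itself speaks of clinical visits in general.

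**Step 5: effect on the AUC.** The protocol gives no rate of smoking among eligible snus users and no figure for the nicotine a cigarette would add. The effect cannot be calculated.

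**The case against.** Four arguments weigh on the other side.

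**Loose drafting.** The quotation mark opened in criterion 1 is never closed, and the sentence can be read as naming two sources by which smoking is established. Site staff may well apply it that way. This is plausible, but the text does not say it. Section 8.2 forbids eligibility waivers, so an exclusion rule should have one meaning. If 'or' was intended, the correction is uncontroversial.

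**Other routes exist.** A reader might infer that a subject who denies smoking can never be excluded whatever the CO, or that none of the 288 readings could ever remove a subject or session. The protocol does not support that. Criterion 12, inclusion criterion 4 (willing and able to comply), withdrawal under Section 8.10.1 and the deviation review under Section 16.3.2 are all available to someone who sees a high CO. What stands is that they depend on judgement and none mentions CO. In an open study a rule fixed in advance is preferable.

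**The session procedure covers admitted smoking.** A subject who admits smoking cannot truthfully certify abstinence under Section 8.1. This weakens the second-row example at treatment visits. It does not remove the mismatch between the entry criterion and the restriction.

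**Limited effect on the endpoint.** A reader might also infer that the primary comparison is biased. Treatment order is randomised within subject, and nothing links undisclosed smoking to one product. A pre-dose nicotine sample is drawn at every session, so residual nicotine would be visible; its use may be set out in the SAP, which is not shown. Snus used before a session is another contamination route, and since smokeless use involves no combustion (Section 6.1), CO would not address it. This argument stands: what can be expected is mainly noise, and the fix protects the AUC only in part.

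**Conclusion.** The point holds as a defect in a stated rule. Taken literally, criterion 1 excludes in one of four combinations, gives a raised CO no effect on a subject who denies smoking, and is looser than the 24-hour restriction in Sections 8.1 and 8.8.1. No other passage ties a consequence to CO.

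Its reach is limited. It concerns criterion 1 and the absence of a stated CO rule after entry, and does not mean that an investigator is powerless. About 72 of up to 288 readings bear on entry, assuming 36 subjects and full attendance. The likely consequence is background nicotine and added variability in the AUC, of a size the documents do not allow to be estimated. Bias between products is not shown.

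The conclusion rests on the ordinary conjunctive reading of 'and'. If the sponsor meant two alternative grounds, the wording still needs changing. The correction is worth making because it is specific and nearly free, though nothing here shows that the primary result is in danger.

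**What to change.** 1. In Section 8.7, criterion 1, and in the synopsis, replace 'and' with 'or', so that either self-reported smoking in the last 24 hours or exhaled CO above 10 ppm meets the criterion. Close the open quotation mark at the same time.
2. Reconcile the new wording with the smoking restriction in Sections 8.1 and 8.8.1 and with Section 10.2.13, which should refer to the threshold.
3. State in advance that CO above 10 ppm at a treatment visit is recorded as a breach of the smoking restriction and assessed as a protocol deviation for the PK analysis set under Section 16.3.2.

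The cost is one word in two places and a sentence or two; CO is already measured, so no new procedure is needed. The downside is that a few more subjects may fail screening, or a few sessions may be flagged.

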8.8 Restrictions during the study

The subjects must be willing to comply to the following restrictions during the entire study duration *i.e.*, from screening to the last Follow-up Visit.

8.8.1 General restrictions

- Subjects shall abstain from snus and all other nicotine containing products from 8.00 p.m. the night before each study day.
- Subjects shall abstain from smoking the last 24 hours before each study day.
- The subjects are not allowed to eat or drink or use any other mouth related procedure (e.g. tooth brushing) 30 minutes before dose administration, during application of investigational products and 30 minutes after the investigational product have been taken out. ³.
- The female volunteers are expected to be sexually abstinent or use non-systemic contraceptives to prevent pregnancy during the study period.

- Abstain from use of Methyl salicylate containing products, e.g. ointments, mouth wash and chewing gum.
- Abstain from drugs of abuse from Screening to the Follow-up visit.
- The subjects must not donate blood or plasma during the study until three months after the Follow-up Visit.
- Study subjects are not allowed to participate in any other clinical study during the study period i.e screening to follow up.

8.8.2 Prior and concomitant therapy

Female systemic contraceptives e.g. birth control pills, injectable steroids, vaginal ring, transdermal patch and contraceptive implants are not allowed in the study.

Other concomitant medications or therapies, including herbal remedies, vitamin supplements and over-the-counter (OTC) products, will be allowed during participation in the study.

8.9 Screen failures

Screen failures are defined as subjects who consent to participate in the clinical study but are no subsequently randomised/entered in the study. A minimal set of screen failure information is required to ensure transparent reporting of screen failure subjects/patients to meet the Consolidated Standards of Reporting Trials (CONSORT) publishing requirements ad to respond to queries from regulatory authorities. Minimal information includes demography, screen failure details and eligibility criteria.

Subjects/patients who do not meet the criteria for participation in this study may be rescreened.

8.10 Criteria for subject/patient withdrawal

8.10.1 General withdrawal criteria

Subjects are free to discontinue their participation in the study at any time and for whatever reason without affecting their right to an appropriate follow-up investigation or their future care. If possible, the reason for withdrawal of consent should be documented.

Subjects may be discontinued from the study at any time at the discretion of the Investigator for any of the following reasons:

- Severe non-compliance to study protocol procedures, as judged by the Investigator and/or Sponsor
- Subject is lost to follow-up. A subject will be considered lost to follow-up if he/she fails to come for 2 number of scheduled visits and if he/she is not possible to contact by site staff despite several attempts.
- Significant AEs posing a risk for the subject, as judged by the Investigator and/or Sponsor

